5 STUDY PROCEDURES

All local and regional regulatory requirements will be fulfilled prior to center activation and enrollment of subjects into the study. Each study site must have written documentation of site and investigator readiness, including (but not limited to):

- Medical Ethics Committee (MEC), Institutional Review Board (IRB) or Head of the Medical Institution written approval of the current version of the Clinical Investigation Plan and Patient Informed consent/Patient Data

Release OR written documentation from the investigator stating approval is not required OR a written waiver from the MEC/IRB must be on file with the sponsor

- When (MEC)/IRB or Head of the Medical Institution written approval is submitted to Medtronic the following needs to be included:
 - The approval letter must contain enough information to identify the version/date of the documents approved or it must be retrievable from the submission letter.
 - Approval letter must be accompanied by a roster or written documentation that center staff participating in the study did not participate in the approval process
- Competent Authority approval or notification (if required)
- Investigator Curriculum Vitae on file with the sponsor (signed and dated as required per geography/country)
- Signed/dated Clinical Trial Agreement on file with the sponsor
- Signed/dated documentation of training of required personnel

All clinical investigators managing the subjects must be qualified practitioners that will be involved in the diagnosis and/or treatment of subjects with SND. All implanting physicians must be experienced in the handling of market released pacemakers from the Medtronic family of devices. All participating Clinicians will complete study training regarding the Informed Consent Process (if applicable), case report forms and Clinical Investigation Plan.

Medtronic will inform the investigator in writing when all requirements have been fulfilled for center activation.

The following study equipment may be useful to have available at each center to support study activities:

- Electrocardiography machine
- Echocardiography machine
- Holter monitor, Event Monitor or Reveal
- Ergometer or treadmill.

5.1 Informed Consent/Patient Data Release Process

Patient Informed Consent(PIC)/Patient Data Release (PDR) is defined as legally effective, documented confirmation of a subject's (or their legally authorized representative or guardian) voluntary agreement to participate in a particular clinical investigation after information has been given to the subject on all aspects of the clinical investigation that are relevant to the subject's decision to participate.

A PDR can only be used when ethics committee approval of the study is not needed or when local laws allow.

Prior to enrolling patients, each investigational center's Medical Ethics Committee (MEC), Institutional Review Board (IRB) or Head of the Medical Institution must, if required by local laws and regulations, approve the Clinical Investigation Plan (CIP) and Patient Informed Consent/Patient Data Release (PIC/PDR). If MEC/IRB approval is not required by local laws and regulations then written documentation from the investigator stating this or a waiver from the MEC/IRB must be sent to Medtronic. Any changes to the PIC/PDR consent must be approved by Medtronic and the MEC/IRB or Head of the Medical Institution reviewing the application before being used to consent a prospective study subject. The document(s) should be controlled (i.e. versioned and/or dated) to ensure it is clear which version(s) were approved by the MEC/IRB or Head of the Medical Institution.

Prior to initiation of any study-specific procedures, subjects (or their legally authorized representative or guardian) must sign and date the data protection authorization and/or other privacy language where required by law and the MEC/IRB or Head of Medical Institution and Medtronic approved Patient Informed Consent/Patient Data Release. A copy of the PIC/PDR form or a signed copy where required by law, will be given to all subjects (or their legally authorized representative or guardian) in a language he/she is able to read and understand.

The process of obtaining patient informed consent shall:

- Avoid coercion and undue influence of subjects to participate
- Answer all questions to the subject's satisfaction
- Not waive or appear to waive subject's legal rights
- Use language that is non-technical and understandable to the subject
- Provide ample time for the subject to consider participation
- Include a dated signature of the subject acknowledging that their participation in the study is voluntary
- Include a dated signature by the clinical investigator or authorized designee (if required)

If the PIC/PDR is obtained the same day the subject begins participating in study-related procedures, it should be documented in the subject's case history that consent was obtained prior to participation in any study-related procedures.

In the event the subject cannot read and/or write, witnessed (impartial third party) informed consent will be allowed, provided detailed documentation of the process is recorded in the subject's case history, the witness was present during the entire discussion and the witness signs and dates the PIC/PDR to attest that the information was accurately explained, and clearly understood by the patient and

that consent was freely given. The original or a copy of the signed PIC/PDR must be filed in the hospital/clinical chart or with the subject's study documents. A copy of the signed PIC/PDR and data protection authorization/or other privacy language where required by law must be provided to the subject.

The PIC/PDR consent form and data protection authorization and/or other privacy language where required by law must be available for monitoring and auditing.

Any Medtronic Field personnel who supports the study must be able to review the subject's signed and dated consent form and verify it's completeness prior to proceeding with study related activities. In the event the Medtronic Field personnel identify a consent as being incomplete, the study activities will not be allowed to occur until the consent of the subject can be adequately and appropriately obtained.

5.2 Data Collection

Table 1 depicts the data collection requirements for the study.

Table 1: Data Collection and Study Procedure Requirements at Subject Visits

Study Procedure	Enrollment/Baseline	Diagnostic Assessment	Implant	Scheduled Follow Up
Informed Consent/Medical Release	X			
Inclusion/Exclusion	X			
Demographics	X			
Medical History	X			
Symptoms	X			
Vitals (HR, BP)	X			
Cardiovascular Medications	X	X	X	
Referral information	X	X	X	
Diagnostic tests/results	X (if applicable)	X		
Blood labs		X		
Final Diagnosis		X		
Device Indication		X		
Pt Education Utilized		X		
Treatment Decision		X		
System Information			X	
Device Programming			X	
Save to disk [∞]			X	
Patient Survey*			X	X
Caregiver Survey [†]			X	X
Death	As they occur			
Reason for Exit				
Study Deviation				

∞ A pre-discharge save to disk needs to be submitted to Medtronic, if available

* The patient survey is only completed for those patients implanted with a market released pacemaker from the Medtronic family of devices.

† The caregiver survey is only completed by consenting caregivers of subjects implanted with a pacemaker from the Medtronic family of market released devices.

5.3 Enrollment/Baseline Procedures

The investigator or designated study coordinator will evaluate patients for inclusion and exclusion criteria. Patients who meet these criteria may be invited to participate in the study. Each study subject or legal representative must sign an informed consent/Patient Data Release prior to any study procedures taking place.

Non-Implanting Physician/Site: Enrollment is anticipated to occur prior to a final diagnosis of the patient being known, however, the patient may be enrolled at any time the IMPROVE Brady inclusion/exclusion criteria are met.

Implanting Physician/Site: If the patient was enrolled in IMPROVE Brady by a referral physician/center and then referred to an implanting physician/center, also participating in the IMPROVE Brady study, an additional study consent does not need to be obtained. If the patient was not previously enrolled in the study then the patient may be enrolled at any time the IMPROVE Brady inclusion/exclusion criteria are met.

When a subject signs and dates the patient consent form/Patient Data Release, he/she is considered a subject enrolled in the study. The date the subject signed the consent form must be reported in the CRF.

The Baseline assessment will be utilized to collect subject demographic data, cardiovascular medical history, symptoms, vital signs, cardiovascular medication use and referral information.

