5.4 Diagnostic Assessment Visit(s)

A diagnostic assessment is any post enrollment visit to the study center for continued diagnostic assessment or management. During these visits information about utilization of diagnostic tests, results and cardiovascular medication use will be collected. Information about the final diagnosis and treatment decision will also be collected during the diagnostic assessment visit. Within each geography/country, collection of the diagnostic assessment visit data will be complete:

- When the subject meets study exit criteria
- 6 months after the last Phase I enrollment for Phase I subjects
- 6 months and after the last Phase II enrollment for Phase II subjects.

The study protocol does not dictate when the Diagnostic Assessment(s) is/are to occur.

Any patient meeting an SND indication with a treatment plan that includes being implanted with an IPG device must have blood drawn to assess for untreated hypothyroidism (TSH & T4 exceeding normal limits) and anemia (HGB<10), if it

was not already done during the diagnostic assessment as part of the site's standard of care.

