4.2.2. Secondary Objective #2

Evaluate the change in the time to diagnosis of SND before and after intervention.

4.2.2.1. *Endpoint Definition*

Time to diagnosis in days (date of diagnosis – date of enrollment); number of visits to diagnosis

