8.5.1.1. Analysis Methods

A. Statistical Methodology

To compare the proportion of subjects with an SND diagnosis pre-intervention (Phase I) to the proportion post-intervention (Phase II), a chi-square test will determine statistical significance. The proportion of subjects diagnosed will be evaluated at multiple time points because the time to diagnosis is expected to vary by geography. Thus, times are pre-specified starting at 6 months and any additional 6-month interval thereafter for which there is sufficient follow-up data available to compare study phases.

Proportions calculated at all available time points will be reported. Additionally a Poisson regression will compare the average number of subjects with an SND diagnosis in Phase I and Phase II where the subject time in study is treated as an offset in the model. The above described tests will be performed only for subjects in the South Asia geographical region as per section 6.

[REDACTED]

[REDACTED]

This document is electronically controlled. Printed copies are considered uncontrolled.

Confidential

[REDACTED]

[REDACTED]

[REDACTED]

B. Determination of Patients/Data for Analysis

All subjects that are enrolled in the study will be included in the determination of the proportion estimates. The proportion estimates will be calculated based on information from fixed time points at 6 months of follow-up, 12 months of follow-up, and any additional 6-month interval thereafter for which there is sufficient follow-up data available to compare study phases. The number of subjects that obtain an SND diagnosis by pre-specified time point $t = 6, 12, \text{ etc.}$, is included in the numerator and the number of subjects enrolled is included in the denominator.

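### Patients may be enrolled after SND is already known and still count as diagnosed in Primary Objective 1, so a difference between phases in that share would bias the diagnosis and time-to-diagnosis comparisons

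*Protocol*

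**What the plan says.** **Enrolment timing.** For non-implanting sites Protocol 5.3 states an expectation and then relaxes it: "Enrollment is anticipated to occur prior to a final diagnosis of the patient being known, however, the patient may be enrolled at any time" the criteria are met. For implanting sites it states no expectation about diagnosis: "If the patient was not previously enrolled in the study then the patient may be enrolled at any time" the criteria are met. The rule common to both is that "the patient may be enrolled at any time the IMPROVE Brady inclusion/exclusion criteria are met". Protocol 4.2 does not list a known SND diagnosis among the exclusions. Protocol Table 1 (section 5.2) provides for diagnostic results that already exist at baseline: "Diagnostic tests/results X (if applicable) X".

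**Where the diagnosis is recorded.** Table 1 places the final diagnosis at the Diagnostic Assessment, and Protocol 5.4 explains: "A diagnostic assessment is any post enrollment visit to the study center for continued diagnostic assessment or management". A diagnosis known before consent can therefore be entered as a study diagnosis.

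**Primary Objective 1 (PO1).** On the denominator, SAP 8.5.1.1 B says: "All subjects that are enrolled in the study will be included in the determination of the proportion estimates". The numerator is "The number of subjects that obtain an SND diagnosis by pre-specified time point". SAP 4.1.1.1 treats a subject as diagnosed if any SND response is selected on the Diagnosis Form. None of these rules sets a lower bound at the enrolment date.

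**Secondary Objective 2 (SO2).** SAP 4.2.2.1 defines the endpoint as "Time to diagnosis in days (date of diagnosis – date of enrollment"), and no readable rule covers diagnoses that precede enrolment.

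**The concern.** PO1 is meant to show whether the workshop and toolkit improve the diagnosis of SND in patients who present with possible SND. Subjects already diagnosed at consent carry no information on that question, yet each adds one to both numerator and denominator.

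An equal share in both phases would create no spurious difference. The design is sequential, however, and the investigators who receive the training also decide when to approach patients in Phase II. If the stage of work-up at consent changes between phases, PO1 changes even when undiagnosed patients are diagnosed at the same rate as before. SO2 is exposed in the same way, because such subjects add very short times to diagnosis.

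The safeguards in the plan do not separate this out. Protocol 4.4 names subject selection as a source of bias but has no measure for stage of work-up. Using centres as their own control does not help if a centre changes when it enrols. The interrupted time series model in SAP 8.2.1 has a linear time term and a phase indicator, so a step change in enrolment timing at the start of Phase II would be attributed to the phase indicator.

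**Working it through.** **Inputs** (SAP 8.5.1.2 and the matching text in Protocol 11.1): 500 Phase I and 1000 Phase II subjects, SND at 6 months 20% versus 28%, type I error 0.05, power 0.90. Sidedness is not stated and is taken as two-sided.

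**1. The plan's own figure.** With the pooled-variance test:
- Pooled proportion = (100 + 280)/1500 = 0.2533.
- SE under no difference = √(0.2533 × 0.7467 × (1/500 + 1/1000)) = 0.0238.
- SE under the alternative = √(0.20 × 0.80/500 + 0.28 × 0.72/1000) = 0.0228.
- Power = Φ((0.08 − 1.96 × 0.0238)/0.0228) = 0.93, or 0.92 with continuity correction.

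The smallest increase detectable at 90% power is 7.6 to 7.8 points. This agrees with the stated 8%.

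**2. Effect of pre-diagnosed subjects.** Let f be the share already diagnosed at consent and p the diagnosis rate among the rest. The observed proportion is f + (1 − f)p. With p the same in both phases, the spurious difference is (f₂ − f₁)(1 − p), which is zero when f₁ = f₂.

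**3. Rejection probability with no true effect** (p = 20%, f₁ = 0; both are assumptions):

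| Phase II share already diagnosed | Expected Phase II proportion | Chi-square significant |
|---|---|---|
| 0% | 20.0% | 5% |
| 2% | 21.6% | 10% |
| 3% | 22.4% | 18% |
| 5% | 24.0% | 41% |
| 8% | 26.4% | 79% |
| 10% | 0.10 + 0.90 × 0.20 = 28.0% | 93% |

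Simulation of 200,000 trials gave 5.0%, 41.4% and 92.9% at 0, 5 and 10 points. The lowest observed Phase II proportion that is significant against 20% is 24.6%. The shift that moves the expectation there is 0.046/0.80 = 5.75 points.

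**4. Some pre-diagnosed subjects already in Phase I.** If the 20% Phase I proportion already includes a share f₁, then p = (0.20 − f₁)/(1 − f₁), and the shift needed for 8 points is 0.08/(1 − p):
- f₁ = 5%: p = 15.8%, shift 9.5 points.
- f₁ = 10%: p = 11.1%, shift 9.0 points.
- f₁ = 15%: p = 5.9%, shift 8.5 points.

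If instead p stays at 20% and the share rises from 10% to 20%, the expected proportions are 28% and 36%, with 88% rejection.

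**5. Poisson analysis.** Assume that pre-diagnosed subjects contribute almost no person-time and all others 0.5 years. A 10-point shift then moves the rate from 0.20/0.5 = 0.40 to 0.28/(0.90 × 0.5) = 0.62 per person-year, above the planned 0.56.

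**The case against.** Several stronger readings are tempting, and the documents do not support them.

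- **That a small shift suffices.** A reader might infer this from the open enrolment rule. Reproducing the full target takes 8.5 to 10 points, which from a Phase I share of zero means about 100 of 1000 Phase II subjects. A 2-point shift raises the false-positive rate only to about 10%.
- **That PO1 is biased, and upward.** The same rule governs both phases. Training could lead to later consent, once SND is recognised. It could equally prompt earlier or broader enrolment of suspected cases, which would lower the share. The documents give no data on the share in either phase.
- **That negative times to diagnosis will occur.** This depends on which date the case report form records. The forms were distributed separately (Protocol Appendix B). If the recorded date is that of the post-enrolment visit, times would not be negative, and a filter on that date would miss the very subjects it is meant to find.
- **That every diagnosis on or before the consent date should be removed.** Entry requires symptoms together with a slow rhythm or a history of exercise intolerance, and symptomatic sinus bradycardia is a qualifying diagnosis. A genuine same-day diagnosis is therefore possible, and it may be an effect of the intervention. Removing such diagnoses could discard true successes unevenly by phase.
- **That PO1 should pass or fail on the restricted set.** SAP 4.1 calls the study exploratory, with no performance requirements for the primary objectives.

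Three further points on the other side are fair. The plan collects referral information and existing test results at baseline, and SAP 8.5.4.1 describes visits to diagnosis by phase and type of enrolling physician. Parts of SAP 8.5.1.1 and 8.5.4.1 are redacted and could hold a handling rule. The magnitudes use planning figures, whereas SAP section 6 now limits phase comparisons to South Asia and Phase II size was to be recalculated.

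These points narrow the concern but do not remove it. The permission is explicit, and the readable population and endpoint rules do not neutralise it.

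**Conclusion.** The point holds as a vulnerability in PO1 and SO2. The all-enrolled analysis cannot distinguish better diagnosis of undiagnosed patients from a change in how many were already diagnosed when they consented. The sizes calculated above rest on the planning rate and sample sizes, on an unchanged rate among undiagnosed enrollees and, except where varied, on no pre-diagnosed subjects in Phase I. Whether the share changed, and in which direction, can be settled only from the trial data. The issue warrants a pre-specified check and does not invalidate the primary analysis.

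**What to change.** In SAP 8.5.1.1 and 8.5.4.1:

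1. Report the share of subjects whose SND diagnosis predates consent, by phase and by implanting versus non-implanting site.
2. Pre-specify a sensitivity analysis of PO1 and SO2 that excludes subjects with a diagnosis dated strictly before the consent date and keeps same-day diagnoses. Add a second version that also excludes same-day diagnoses. Show both beside the all-enrolled analysis.
3. If the form records only a visit or form date, identify pre-diagnosed subjects from the baseline diagnostic results and referral information already collected.
4. State that a PO1 difference will be interpreted as improved diagnosis only with this result reported alongside. Do not make it a pass/fail condition.

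The cost is SAP wording, slightly fewer subjects in the sensitivity sets and a little more analysis work. If step 3 is needed, classifying subjects from baseline data takes somewhat more effort.

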5.4 Diagnostic Assessment Visit(s)

A diagnostic assessment is any post enrollment visit to the study center for continued diagnostic assessment or management. During these visits information about utilization of diagnostic tests, results and cardiovascular medication use will be collected. Information about the final diagnosis and treatment decision will also be collected during the diagnostic assessment visit. Within each geography/country, collection of the diagnostic assessment visit data will be complete:

- When the subject meets study exit criteria
- 6 months after the last Phase I enrollment for Phase I subjects
- 6 months and after the last Phase II enrollment for Phase II subjects.

The study protocol does not dictate when the Diagnostic Assessment(s) is/are to occur.

Any patient meeting an SND indication with a treatment plan that includes being implanted with an IPG device must have blood drawn to assess for untreated hypothyroidism (TSH & T4 exceeding normal limits) and anemia (HGB<10), if it

was not already done during the diagnostic assessment as part of the site's standard of care.

5.5 Implant Visit

The implant visit is when the IPG is implanted in the study subject and will only occur for those subjects meeting the ACC/AHA/HRS and ESC pacing indications. The implant will be performed according to the hospital's standard implant practice. IMPROVE Brady does not have device programming requirements. Information about the procedure, the device, and how the device was programmed will be collected. A pre-discharge save-to-disk with a final interrogation will also be collected and submitted to Medtronic, if available.

(Phase II only)

At the implant visit the study subjects being implanted with a market released pacemaker from the Medtronic family of devices will complete a patient survey prior to implant to assess their quality of life and functional status. During this visit the subject's caregiver will be asked to complete a Caregiver survey after signing a PIC/PDR. The purpose of the caregiver survey is to assess how providing care to the patient impacts the caregiver.

5.6 Scheduled Follow-up Visit (Phase II only)

The scheduled 6 months post-implant follow up visit is required for subjects that received a market released pacemaker from the Medtronic family of devices and their participating caregiver. During this visit the subject with the IPG will complete the patient survey and the caregiver will complete a caregiver survey. The caregiver completing the survey must be the same caregiver that completed the pre-implant caregiver survey.

5.7 Study Exit

Subjects may be exited from the study for any of the following situations, including but not limited to:

- Subject does not meet an indication for pacing therapy
- Subject meets an indication for pacing but not a SND indication for pacing therapy
- Subject has met a SND indication for pacing therapy and did not receive a market released pacemaker from the Medtronic family of devices
- Subject has met a SND indication for pacing therapy but will not be receiving pacing therapy
- Subject has completed the final scheduled follow-up visit.

- Geography/country completion of Phase I follow-up
- Study Closure
- Subject lost to follow-up
- Subject death
- Subject did not meet inclusion/exclusion criteria
- Subject chooses to withdraw (e.g., consent withdrawal, relocation to another geographic location)
- Investigator deems withdrawal necessary (e.g., medically justified, failure of subject to maintain adequate study compliance)

